3. STUDY DESIGN

3.1. Design

This is a definitive, single-blind cluster randomized controlled - superiority trial embedded within the primary care system to assess the real-world effectiveness of a package of tertiary interventions before and during gestation in reducing the incidence of fetus and birth defects compared with the standard usual perinatal care. We will

recruit prepare-for-pregnancy women and their husbands through the pre-pregnancy eugenics examination clinic. Blood samples will be collected for examining RBC folate concentrations at enrollment. According to the randomization plan, participants recruited from the same community health care centre (cluster) will receive the same intervention, and clusters allocated to the two arms will receive the standard care or a serious experimental care procedure. The methods and protocols for measuring the primary outcome and the secondary outcomes in the two arms will follow the same clinical routines.

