3.3. Interventions

Experimental interventions: usual care plus additional procedures

- Before conception:

Participants will be examined for serum and RBC folate concentrations at enrollment to identify those with insufficient RBC folate concentration (<400ng/mL). Based on reviewing of folate supplement status of from the participant-administered questionnaire, a trained nurse will call the participant to inform them the RBC folate concentration and folate metabolism ability evaluated by one's genotypes of MTHFR C677T variant, and provide individualized folic acid supplementary instructions to improve folate status before get pregnant. A second RBC folate test is booked.

- During gestation -- Green channels for confirmation of fetus defects and a following genetic and clinical consulting:

In the both arms, fetus and infants with screen positive of fetus defect(s) will be referred via a green channel to approach an authorized tertiary obstetric hospital to achieve timely further routine comprehensive assessments and confirmative diagnosis. Then the participants with established diagnosis of fetus defects will be referred to a multi-discipline paediatric expert team for a deep consultation about possible postnatal treatments in the future to avoid unnecessary abortions.

- **After delivery:**

The participants from the experimental arm will additionally provide timely referral to a prespecified team of pediatrician experts for timely medical treatment or scheduled follow-up.

Standard tertiary interventions of birth defects (control arm, usual care):

Couples eligible for reproductive policy are entitled to routine health cares including general health cares (health education, medical history inquiry, physical examinations, consulting guidance and pregnancy outcome follow-up) and medical examinations (laboratory examinations, virus screenings and image examinations). But nutrients status is not included in these examinations, such as folate, vitamin B12 and microelements, etc. Regular antenatal cares are required, such as deformity screening by ultrasound. Routine neonatal screenings are conducted to diagnose infant with birth defect(s) timely.

Intervention procedures of FOID study

	Experimental arm Procedures in addition to the usual care	Control arm Usual care
Before conception		
Preconception at enrollment	RBC folate test Inform and instruction about folic acid supplementation via phone interview	Routine physical examination and routine blood tests

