3.5. Sample Size

Sample size calculation was performed based on the primary outcome- the incidence of a composite rate of fetus, still birth, or birth defects. The proportion of primary endpoint was conservatively estimated to be 8% in the control arm according to two recent observational studies^{6,7} and 4% in the experimental arm (or 50% reduction) based on the findings of a meta-analysis of randomized intervention trials of folic acid supplementation intervention in folate-deficient population⁸. With cluster size of 100 subjects per centre, K coefficient of 0.23, a power of 85 % and a 5 % level of type I error, 22 clusters (2200 patients or 1100 in each arm) will be required. To allow for a 10 % dropout rate, at least 111 subjects (2446 patients or 1223 in each arm) will be recruited in each centre.

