4. ANALYSIS POPULATIONS

4.1. Study Population Data Sets

Two study populations will be considered in the analysis as follows:

- **Intent-to-Treat (ITT) population**

ITT population will be defined as the pregnant women among preparing-for-pregnancy couples that were recruited since November 1, 2018, from the randomized clusters and finally get pregnant. Participants will be excluded from the ITT analysis if the primary outcome is missing, forming a modified ITT population (mITT).

- **Per protocol (PP) population**

PP population will only include participants who received the treatments according to the protocol. Specifically,

- Participants of the experimental group: will be considered non-compliant with the preconception intervention if their RBC folate levels do not reach the target level (400 ng/ml) at the 1st antenatal visit.
- Participants in the control group received the usual care only, no non-complaints will be defined.
- Participants in both groups who do not have RBC folate levels measured at the 1st antenatal visit will not be included in the PP population.

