5.1.2. Sensitivity analyses of the primary outcome

- **PP analysis of the primary outcome**

The same analysis of the primary outcome will be performed in the PP population using a GEE model (described in 5.1.1).

- **Covariate adjusted analysis of the primary outcome**

A GEE model used for the analysis of the primary outcome in Section 5.1.1 will also be used for covariate adjusted analysis using inverse probability of treatment weighting (IPTW) approach. The covariates will include age (continuous variable), ethnic (binary variable), body mass index (continuous variable), adverse pregnant history (binary variable), parity (continuous variable), exposure to smoking (mother or father's smoking status, binary variable), total cholesterol (continuous variable), and RBC folate level (continuous variable) at baseline to estimate adjusted risk ratio and 95% CI. Covariate adjusted analysis will be performed on both ITT and PP populations.

We will first calculate a propensity score with treatment as the dependent variable (1 for the experimental group and 0 for the reference group), and all covariates listed above as independent variables through a logistic regression model with a random effect for the center, and then perform an IPTW analysis (weighted GEE model). The adjusted risk ratio between the two groups and its two-sided 95%CI will be estimated.

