5.1.3. Subgroup analysis of the primary outcome

A GEE model used for the analysis of the primary outcome in Section 5.1.1 will also be used for subgroup analysis of the primary outcome.

Subgroup analyses will be performed on age (< or \geq 35), ethnic (Han ethnicity or other

ethnicities), BMI ($<$ or $\geq 24\text{kg}/\text{m}^2$), presence of adverse pregnant history (Yes, No), exposure to smoking (Yes, No), total cholesterol ($<$ or $\geq 5.2 \text{ mmol}/\text{L}$), RBC folate status at baseline ($<$ or $\geq 400 \text{ ng}/\text{mL}$). Subgroup analyses may also base on categorized variables of the above continuous variable based on median value to make sample sizes of the categories comparable to achieve greater power.

Assessment of the homogeneity of treatment effect by a subgroup variable will be conducted by a GEE with the treatment, subgroup variable, and their interaction term as predictors, center as cluster, and the *P*-value presented for the interaction term.

Subgroup analysis will be performed on both ITT and PP populations.

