6.6. Missing Data

Missing baseline covariates will be imputed using simple imputation methods in the covariate adjusted analysis based on the covariate distributions, should the missing values for a particular covariate be less than 5%. For a continuous variable, missing values will be imputed from random values from a normal distribution with mean and SD calculated from the available sample. For a categorical variable, missing values will be imputed from random values from a uniform distribution with probabilities P_1, P_2, \dots , and P_k from the sample. Seed for the imputation will be set as 128.

If the missing values for a covariate are $\geq 5\%$ then they will be imputed using Markov chain Monte Carlo (MCMC) methods using SAS PROC MI.

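### SAP 3.3 and 4.1 contradict each other on RBC folate at the first antenatal visit in control women; taken literally, the per-protocol population has no controls

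*SAP*

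**What the plan says.** **First antenatal visit.** The table in SAP 3.3 has one column for experimental procedures added to usual care and one for usual care. The RBC folate test at this visit stands in the first; the control entry is routine clinical examinations. The usual-care text in 3.3 adds: "But nutrients status is not included in these examinations, such as folate, vitamin B12 and microelements, etc". SAP 4.1 nevertheless makes the measurement a condition of PP entry in both groups: those "who do not have RBC folate levels measured at the 1st antenatal visit will not be included in the PP population". The preceding bullet in 4.1 says that controls had usual care only and defines no non-compliance for them. The Table 2 shell in section 7 reports first-visit RBC folate for both treatments.

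**Enrolment.** The Introduction and 3.3 present the enrolment test as something the experimental arm receives. Section 3.1, describing recruitment in general, says "Blood samples will be collected for examining RBC folate concentrations at enrollment" and names no arm. Appendix 2.1 lists first-test RBC folate in the same list as the intervention/control flag.

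**Use in the analyses.** The IPTW analysis in 5.1.2 includes "RBC folate level (continuous variable) at baseline to estimate adjusted risk ratio". Section 5.1.3 has a subgroup by "RBC folate status at baseline", cut at 400 ng/mL. Both analyses are planned for the ITT and PP populations. In the covariate-adjusted analysis, 6.6 says of covariates with 5% or more missing: "then they will be imputed using Markov chain Monte Carlo (MCMC) methods using SAS PROC MI".

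**The concern.** A PP comparison needs women in both arms who can meet its entry rule. Here the rule depends on a measurement that the SAP's description of procedures gives to one arm only. A programmer who applied 4.1 to data collected as 3.3 describes would obtain a PP set made up of experimental women alone, with no risk ratio to estimate. One of the SAP's two analysis populations would be unusable. A replacement PP definition chosen after allocation is known would be post hoc.

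The baseline value raises a second, weaker question. The IPTW model and the 400 ng/mL subgroup need it in both arms, and the SAP does not say consistently that both arms have it.

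**Working it through.** **1. Planned numbers, reproduced first.** Inputs from SAP 3.5: 8% against 4%, cluster size m = 100, k = 0.23, power 85%, type I error 5% (two-sided assumed, as the SAP does not say). Cluster formula for proportions:

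c = 1 + (t_a + t_b)² × [p0(1−p0)/m + p1(1−p1)/m + k²(p0² + p1²)] / (p0 − p1)²

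- Bracket: 0.000736 + 0.000384 + 0.0529 × 0.0080 = 0.0015432.
- Divided by 0.04² = 0.0016: 0.9645.
- t quantiles on 20 df: (2.086 + 1.064)² = 9.92, and 9.92 × 0.9645 = 9.57.
- c = 10.57, so 11 clusters per arm, or 22 in all. This matches the SAP. (Normal quantiles give 9.66, so 10 per arm.)
- Dropout: 1100 / 0.90 = 1222.2, so 1223 per arm and 2446 in all. This also matches.

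The point changes none of these figures. They supply only the denominators below.

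**2. First antenatal visit, passages side by side.**

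| Place in SAP | Experimental | Control |
|---|---|---|
| 3.3 table | RBC folate test | routine clinical examinations |
| 3.3 usual-care text | – | folate status not examined |
| 4.1 PP rule | measurement required | measurement required |
| Section 7, Table 2 | reported | reported |

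Rows 1 and 2 give controls no test; rows 3 and 4 presuppose one. Applying 4.1 to the procedures in 3.3 leaves 0 of about 1100 controls in PP.

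**3. Consequences under each possible state of control testing.**

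| Controls tested at | PP controls | Baseline covariate and subgroup in ITT |
|---|---|---|
| enrolment and first visit | those measured | usable; 3.3 table is wrong |
| enrolment only | 0 | usable |
| neither | 0 | covariate missing for 1100 / 2200 = 50% (same as 1223 / 2446), all in one arm; subgroup and interaction test cannot be fitted |

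In the last row, 50% is ten times the 5% threshold in 6.6, so the MCMC route applies. With no control value observed, the data cannot show how RBC folate differs between arms. Imputed control values would rest on experimental women alone, and adjustment for them would carry no information on control women's folate. Section 6.6 confines imputation to the covariate-adjusted analysis, so it would supply nothing for the subgroup or Table 2.

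**4. Primary analysis.** The GEE model in 5.1.1 has treatment as its only independent variable and is run on the ITT population. RBC folate does not enter it.

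**The case against.** The best defence is that the 3.3 table describes care delivered and is not a schedule of research measurements. It is also not a dependable guide to what controls receive. It shows neonatal CHD screening in the experimental column only, although 2.2.2 says that all newborns are screened. The referral route for positive screens appears under the experimental heading, although the text applies it to both arms. The both-groups wording of 4.1 and the two columns of Table 2 suggest that control measurement may have been intended. Assessment schedules are often left to the protocol, which is not at hand. This stands in part: an empty PP control arm is the literal result, not necessarily the intended one. It does not remove the contradiction, because no procedure passage in the SAP gives controls a first-visit test.

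A reader might go further in three ways that the document does not support.

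- **That baseline RBC folate will be imputed for the whole control arm.** Section 3.1 provides enrolment sampling without naming an arm, and Appendix 2.1 is consistent with testing in both. The 50% figure arises only if the Introduction and 3.3 are read against 3.1.
- **That the appendices show controls to be untested at the first visit.** Appendix 2.2 and the pregnancy block of Appendix 2.1 omit RBC folate for everyone, including experimental women, whom 3.3 does test. The lists are incomplete, and their silence does not separate the arms.
- **That testing controls would undo the usual-care contrast through awareness of the result.** The call that informs women of their result is assigned to the experimental arm, and no passage says that control results are released.

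**Conclusion.** The contradiction over first-visit RBC folate in controls is real, and the SAP alone cannot settle which passage is in error. Followed as written, 3.3 and 4.1 put no control woman in the PP population, so the PP analysis and its covariate-adjusted and subgroup versions cannot be estimated.

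For enrolment the finding is an ambiguity. Missingness across the whole control arm, about 50% overall, is conditional on controls not having been tested then, and assumes arms of equal size as planned.

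Severity is moderate. What is affected is confined to sensitivity analyses, the PP subgroup analyses, one of eight IPTW covariates, one of seven subgroup variables and a descriptive table. The main conclusion, drawn from the ITT GEE model, does not depend on RBC folate.

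**What to change.** Before unblinding, reconcile 3.1, the 3.3 table, 4.1, Table 2 and Appendix 2 so that they state, by arm and by time point, whether RBC folate is measured. Then:

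- **If controls are measured at the first visit:** correct the 3.3 table, add the variable to Appendix 2 for both arms, and show the number measured by arm in Table 2.
- **If they are not:** remove the first-visit measurement requirement for controls from the PP rule, or drop the PP comparison. Removing it leaves experimental women selected on a measurement and controls not, and the report should say so.
- **If baseline values are absent in controls:** take RBC folate out of the IPTW covariates in 5.1.2 and the subgroup list in 5.1.3, and state in 6.6 that a covariate missing by design in one arm is not imputed.

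The cost is SAP wording, with no new data. The downside is that the PP comparison, one covariate or one subgroup may have to be given up if control samples were not assayed.

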4.2. Analysis Close Date

The analysis close date will be the date on which the last participant completed follow-up to achieve the primary outcome and until age of six months.

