2.2. Outcomes

2.2.1. Primary outcome

The primary outcome is the occurrence of fetus defects, stillbirth, and neonatal birth defects identified from the confirmation of pregnancy to 28 days after birth.

- **Description:**

This is a composite outcome that includes a total of 24 types of defects according to the national birth defects surveillance policy, including fetus defects detected by

screening examinations for Down syndrome (DS), NT during early gestation, organ defects identified by routine antenatal ultrasound image examinations during the second trimester, stillbirth occurring during the entire gestation period, and birth defects identified after delivery and diagnosed by clinical examinations including ultrasound examination (Details of 24 defects types see Appendix 1). The primary outcome will be defined as “occurred” if any one of the 24 defects occurs. All examinations to measure the primary outcome will follow current routine protocols. Besides, detailed information on both miscarriages and artificial abortions will be collected, including the time of abortion, reasons for abortion, and antenatal information before an abortion.

- Time Frame: from the confirmation of pregnancy to 28 days after birth.
- Type: binary variable (Yes / No).

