2.2.2. Secondary outcomes

(1) The occurrence of fetus defects

- This is a composite outcome and will be defined as “occurred” if any of the 24 defects are detected by routine ultrasound screening during pregnancy (Details of defects types see Appendix 1).
- Time Frame: from the confirmation of pregnancy to before delivery.
- Type: binary variable (Yes / No).

(2) The occurrence of birth defects

- This is a composite outcome and will be defined as “occurred” if any of the 24 defects are detected by ultrasound examination within one year old (Details of defects types see Appendix 1).
- Time Frame: from birth to one year old.
- Type: binary variable (Yes / No).

(3) The occurrence of infant death or severe organ dysfunctions

- This is a composite outcome and will be defined as “occurred” if either infant death or severe organ dysfunctions occur.
- Time Frame: from birth to 6 months after delivery (can be expanding to the end of the 7th month).
- Type: binary variable (Yes / No).

(4) The occurrence of abortion that related with congenital defects

- Time Frame: from the confirmation of pregnancy to the 28th gestational week.
- Type: binary variable (Yes / No).

(5) Count of fetus defects, stillbirth, and birth defects

- Time Frame: from the confirmation of pregnancy to 28 days after birth.
- Type: Count-Number of events.

(6) Occurrence of confirmed congenital heart defects (CHD)

- All pregnancies will have prenatal ultrasound scans in the second trimester (around 20 to 24 weeks of gestation) performed by trained ultrasound sonographers; abnormal findings will be confirmed by authorized tertiary fetal medical centers. All newborns will have routine neonatal CHD screening, and those screened positive will be subsequently sent for further echocardiographic confirmation. The nomenclature of the International Paediatric and Congenital Cardiac Code (of the Nomenclature Working Group of the International Society for Nomenclature of Paediatric and Congenital Heart Disease) will be used to define CHD.
- Time Frame: from the confirmation of pregnancy to 28 days after birth.
- Type: binary variable (Yes / No).

(7) Occurrence of maternal gestational diabetes (GDM)

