- Pregnant participants will receive a 75-g oral glucose tolerance test during 24-28 gestational weeks, and GDM will be diagnosed if any of the following criteria are met, based on the recommendations of the International Association of the Diabetes and Pregnancy Study Groups Consensus Panel: fasting glucose ≥ 5.1 mmol/L, 1-hour glucose ≥ 10.0 mmol/L, or 2-hour glucose ≥ 8.5 mmol/L.
- Time Frame: during 24-28 gestational weeks.
- Type: binary variable (Yes / No).

(8) Maternal gestational weight gain (kg)

- This outcome will be calculated as body weight at delivery minus weight before pregnancy (self-reported).
- Time Frame: from pre pregnancy to delivery.
- Type: continuous variable.

(9) Maternal weight gain (kg) at early gestation

- This outcome will be calculated as body weight at around 20 gestational weeks minus weight before pregnancy (self-reported).
- Time Frame: from pre pregnancy to 20 gestational weeks.
- Type: continuous variable.

(10) Occurrence of gestational hypertension

- Pregnant participants will undergo blood pressure measurements at each prenatal visit. Gestational hypertension will be diagnosed if systolic blood pressure ≥ 140 and/or diastolic blood pressure ≥ 90 mmHg, based on the recommendations of the International Society for the Study of Hypertension in Pregnancy (ISSHP).
- Time Frame: during pregnancy.
- Type: binary variable (Yes / No).

- (11) Maternal body weight (kg) at 6 months after delivery (Continuous variable)
- (12) Maternal HbA1c (%) at 6 months after delivery (Continuous variable)
- (13) Infant body weight (g) at birth, 42 day, 3 months, and 6 months (Continuous, repeated measurements)
- (14) Infant length (cm) at birth, 42 day, 3 months, and 6 months (Continuous, repeated measurements)
- (15) Infant body mass index (kg/m²) at birth, 42 day, 3 months, and 6 months (Continuous, repeated measurements)
- (16) Medical cost that relates with fetus and birth defects during pregnancy and after birth (Time Frame: from confirmation of pregnancy to one year old after birth) (Continuous variable)

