5.2.1. Analysis of binary secondary outcomes

Binary secondary outcomes will be analyzed with the same strategy and method that is used for the analysis of the primary outcome. GEE model will be performed with treatment as the only predictor and center as cluster effect using binomial distribution and log link function, from which the risk ratio between intervention and the control arm together with 95% CI will be derived.

Non-convergence will be dealt with using the same strategy as for the primary outcome analysis in Section 5.1.1

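### The analysis closes when the last infant is six months old, but two secondary outcomes run to one year and the SAP has no rule for infants with shorter follow-up

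*SAP*

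**What the plan says.** Section 4.2 sets a single analysis close date, when "the last participant completed follow-up to achieve the primary outcome and until age of six months". Section 4.3 describes one cleaning and locking of the database before it goes to the statisticians. No later cut appears anywhere in the SAP.

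The outcome windows compare with that date as follows:

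- Primary outcome (2.2.1): "Time Frame: from the confirmation of pregnancy to 28 days after birth". This fits within the close.
- Secondary outcome (2), birth defects (2.2.2): counted as occurred "if any of the 24 defects are detected by ultrasound examination within one year old", with "Time Frame: from birth to one year old". This runs past the close.
- Secondary outcome (16), medical cost (2.2.2): "Time Frame: from confirmation of pregnancy to one year old after birth". This runs past the close.
- Secondary outcome (3), infant death or severe organ dysfunction (2.2.2): "from birth to 6 months after delivery (can be expanding to the end of the 7th month". The optional extension runs past the close.

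For binary secondary outcomes, section 5.2.1 states that a "GEE model will be performed with treatment as the only predictor and center as cluster effect". Section 5.3 compares total cost between arms as a continuous variable. It accumulates cost up to a follow-up endpoint that it does not define.

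**The concern.** The SAP fixes both the close date and the outcome windows, and they disagree. Six months of infant follow-up are guaranteed at the close, while outcomes (2) and (16) need twelve. The youngest infants cannot supply the second half of the window.

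Nothing in the analysis absorbs this. The count outcome has a follow-up-time offset (5.2.3), but the models for outcomes (2) and (16) have neither an offset nor censoring. Section 6.6 deals only with missing baseline covariates, and section 4.1 excludes participants only for a missing primary outcome. How to treat an infant followed for, say, eight months is left open, and section 3.4 releases the allocation once the database is locked. At stake are the absolute one-year risk of birth defects and the one-year cost and, under further conditions, the comparison between arms for these two outcomes.

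**Working it through.** The SAP states no figure to reproduce. The check compares time windows and then illustrates the size.

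**Inputs from the SAP.** Follow-up guaranteed at the close is 6 months (4.2). The window for outcomes (2) and (16) is 12 months (2.2.2).

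**Assumptions.** The birth period lasts B months, which the SAP does not give. Births are evenly spread over it, and the close falls 6 months after the last birth.

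**Step 1: who is cut short.** An infant born s months before the last birth has 6 + s months of follow-up at the close. This is below 12 when s < 6. For B of at least 6, the affected share is 6/B.

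**Step 2: how much is lost.** The shortfall is 12 − (6 + s) = 6 − s months. Over s from 0 to 6 it averages 3 months, with a maximum of 6. The share of all infant-months lost from the 12-month window is (6/B) × 3/12. All of the loss falls in months 6 to 12, where the share lost is (6/B) × 3/6 = 3/B.

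| B (months, assumed) | Infants with under 12 months, 6/B | Lost from months 0–12 | Lost from months 6–12, 3/B |
|---|---|---|---|
| 12 | 50% | 12.5% | 25% |
| 18 | 33% | 8.3% | 16.7% |
| 24 | 25% | 6.3% | 12.5% |
| 36 | 17% | 4.2% | 8.3% |
| 48 | 12.5% | 3.1% | 6.3% |

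**Step 3: from short follow-up to bias.** Suppose unobserved months were treated as event-free. Let R be the true one-year risk, r the part first detected between 6 and 12 months (evenly over those months), and f = 3/B. The estimated risk is then R − f·r. The SAP gives no value for r, so the bias cannot be sized. It is zero if r is zero, and it is at most a fraction f of R, reached only if every case were first detected after six months.

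**Step 4: the comparison between arms.** With the same birth timing, f is the same in both arms. The risk ratio becomes (R1 − f·r1)/(R0 − f·r0). This equals R1/R0 when late detections form the same share of the risk in both arms. The mean cost difference changes by f·(c1 − c0), where c is the mean cost arising in months 6 to 12 (spread evenly over them). It is unchanged if that cost is the same in both arms.

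**Step 5: after either fix.** With a cut at the last infant's first birthday, or a window ending at an age that all infants reach by the close, the affected share is 0%.

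**The case against.** The strongest objection is that the SAP nowhere says unobserved months are counted as no event or zero cost. That is correct. A reader might infer it, because an ever/never outcome and a running cost total tend to default that way. But section 4.3 asks for missing data to be properly coded, and section 6.3 bases percentages on subjects with data available. These infants could equally be set to missing or excluded. What stands is that no rule exists, not that a wrong rule has been adopted.

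Second, section 2.2.3 includes fetal and birth defects identified up to 28 days after birth. If that rule governed outcome (2), every infant would be complete well before the close. But section 2.2.2 gives one year for outcome (2) both in its definition and in its time frame. The 28-day rule therefore does not remove the conflict. It adds a second one to be reconciled.

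Third, section 5.3 leaves further cost-effectiveness work to a separate plan. The simple comparison of cost between arms remains in this SAP, so the cost point is reduced but not removed.

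Fourth, 6/B is a share of infants, not of defects or cost. Appendix 1 lists mainly structural defects, and section 2.2.3 places ascertainment in pregnancy and the newborn period. Few cases may first appear after six months, so 50% could greatly exceed any effect on the risk estimate. This stands in full.

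Finally, a reader might infer that truncation differs by arm, for example if women in the experimental arm delay conception to raise their folate. Nothing in the SAP shows that birth timing differs, and one close date applies to both arms.

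**Conclusion.** The contradiction holds on the face of the SAP. The close date in 4.2 cannot deliver the one-year windows of outcomes (2) and (16) for infants born in the last six months of the birth period. Under evenly spread births and an assumed birth period of 12, 24 or 36 months, that is 50%, 25% or 17% of infants, who lose 3 months on average and 6 at most.

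The consequences are conditional. If those infants are analysed as though complete, one-year risk and cost may be understated, by an amount the SAP does not allow one to calculate. The risk ratio is distorted only if birth timing or the timing of detection differs by arm. The cost difference is distorted only if birth timing, or the cost arising in the unobserved months, differs by arm. The stronger statement, that the SAP counts lost months as event-free and so biases the results, is not supported.

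The primary outcome and the main conclusion drawn from it are untouched. Two of sixteen secondary outcomes are affected, plus the optional extension of outcome (3). Severity is minor to moderate.

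**What to change.** Amend 4.2 in one of two ways:

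- Keep the one-year windows and add a second data cut at the last infant's first birthday, for outcomes (2) and (16) only. The cost is later reporting of two secondary outcomes.
- Redefine both outcomes to end at one common age that every infant reaches by the close date. The cost is that defects detected and expenses arising after that age are no longer captured.

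Neither option needs extra participants. In the same edit:

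- Reconcile the window of outcome (2) with the 28-day rule in 2.2.3.
- Define the follow-up endpoint for cost in 5.3 so that it matches outcome (16).
- Set the first lock late enough to cover the extension of outcome (3) to the end of the seventh month. A lock at exactly six months would repeat the same fault there.
- State how an infant with incomplete follow-up is handled for these outcomes, so that the choice is not made after the allocation is known.
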